## **4.2. Potential Benefits**

Participants may not derive any benefit at all from participating in the study. At the same time, the extensive genetic, biochemical, and non-invasive imaging evaluation may uncover unknown genetic susceptibilities and/or early identification of variance and deviations from a study subject's baseline profile that may be worthy of further evaluation and testing by the study subject's primary care physician, providing some potential benefits to participants.

## **4.3. Overall Benefit/Risk Ratio**

Given that potential risks are minimal or negligible as described above, and given potential benefits as described above, the overall benefit/risk ratio favors participation in the study.

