#### **3.3.2. Methodology**

Each of the visits include a combination of Medical history and PE, biochemical and “omics” assessments, non-invasive imaging assessments and optional functional assessments and wearables and quantified self-assessments.

*Medical history and PE* The Medical history and PE consists of a comprehensive “History and Physical Examination”, administered by a trained Research Associate. The elements of the history and physical examination are recorded in the Case Report Form (CRF).

- *Pregnancy Testing*

Pregnancy testing consists of a UPT for all WOCBP. The results must be negative for the subject to be able to participate in each visit.

- *Genomic Analysis*

- Whole genome sequencing (WGS) analysis (“DNA”)

- *Biochemical and “Omics” Assessments*

Biochemical and “omics” assessments consist of the following elements, using peripheral blood samples, and potentially urine, stool or saliva samples.

- Whole genome methylation analysis (“DNA methylation”)
- Whole transcriptome sequencing from circulating mononuclear cells (mRNA and miR)
- Proteomics profiling
- Metabolomics profiling
- Conventional biomarker analysis
- Urine analysis and profiling

- *Non-Invasive Imaging Assessments*

Non-invasive imaging assessment consists of the following elements, as directed, and determined by the Medical history and PE and biochemical and “omics” assessment, as described above. Imaging will follow the schedule in the table below, with an “x” indicating all participants and an “[x]” indicating imaging needed for risk-specific participants. Any deviation from the average population may trigger a dedicated organ specific MRI. Imaging may also be done at 18-, 24- and/or 36-month visits, depending on Medical history and PE at each visit, following the schedule at 6 or 12 months.

Imaging Procedure	Baseline	6 mos	12 mos
CT of head	x		
CT Angiogram of head/neck/face/sinus/orbits	x		
MRI of brain with and without contrast	x		x
MR Angiogram of head/neck time of flight			x
MRI of brain without contrast		[x]	
CT of chest, abdomen, and pelvis - mixed A/V	x	[x]	[x]
CT of chest, abdomen, and pelvis - venous only		[x]	x
MRI of spine without contrast (cervical/thoracic/lumbar)	x		x

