Individuals will also undergo CT. CT is a safe imaging method that includes exposure to ionizing radiation with or without contrast agents. The contrast is either given orally, rectally or intravenously. This contrast material can rarely cause medical problems or allergic reactions. Most of these reactions are mild and result in a rash or itchiness. In rare instances, an allergic reaction can be serious, even life-threatening.

During an abdominal ultrasound exam, a trained technician will glide a small device over the participant’s abdomen to take pictures of the tissue under the skin. There are no known side effects from taking part in an abdominal ultrasound exam. Ultrasound tests do not involve radiation and they do not penetrate the skin.

Due to the risk of imaging radiation exposure to a fetus, WOCBP must not be pregnant at any visit.

Individuals will also undergo x-ray imaging. X-ray is an imaging method that includes exposure to a low amount of electromagnetic radiation to take pictures of structures in the body, such as bones.

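### The benefit/risk conclusion of minimal or negligible risk rests on a risk section that names no radiation risk to participants and gives no examination count, while the imaging table marks four CTs per participant by month 12

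*Protocol*

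**What the plan says.** Section 4.3 of the protocol concludes that the benefit/risk ratio favours participation, from the premise "Given that potential risks are minimal or negligible as described above". The synopsis (Study Type) labels the study minimal-risk, and section 4.1 opens with the same assessment.

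On CT, section 4.1 states: "CT is a safe imaging method that includes exposure to ionizing radiation with or without contrast agents". The harms it then describes for CT are contrast reactions, mostly mild but in rare cases serious or life-threatening. For X-ray it mentions a low level of exposure and no harm. The one radiation risk named in the section concerns pregnancy: "Due to the risk of imaging radiation exposure to a fetus, WOCBP must not be pregnant at any visit". For gadolinium, by contrast, it gives reaction rates, including 0.001% to 0.01% for severe anaphylactic reactions.

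The schedule is in section 3.3.2. An x in the imaging table means all participants. A bracketed [x] is explained as "indicating imaging needed for risk-specific participants". After month 12, "Imaging may also be done at 18-, 24- and/or 36-month visits", following the 6- or 12-month column.

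Eligibility (section 3.2.1) runs from age 18 to 90, with or without disease, and section 4.2 says participants may gain no benefit at all.

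**The concern.** A benefit/risk statement that refers back to an earlier description is only as good as that description. Here the description discloses an exposure, calls the procedure safe, and stops. It neither says what the exposure could mean for the participant nor adds up how often it occurs. A reader of section 4 alone could not tell that the table schedules several CTs in the first year, with more possible later.

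This matters because people without disease are eligible and the protocol concedes that they may not benefit, so the risk side has to be stated accurately. Section 8.1 requires the risks of the procedures to be explained at consent, and section 4 is where the protocol sets those risks out. No endpoint or analysis is affected. What is at stake is whether a stated property of the study follows from its own schedule.

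**Working it through.** The protocol gives no count of its own to reproduce, so the check is a direct count of the CT rows in the imaging table of section 3.3.2.

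| CT row | Baseline | 6 months | 12 months |
|---|---|---|---|
| Head CT | x | – | – |
| "CT Angiogram of head/neck/face/sinus/orbits" | x | – | – |
| "CT of chest, abdomen, and pelvis - mixed A/V" | x | [x] | [x] |
| "CT of chest, abdomen, and pelvis - venous only" | – | [x] | x |

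**Non-risk participants (x only)**

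- By month 12: 3 + 0 + 1 = 4.
- Each of the three later visits (18, 24, 36 months) adds 0 CTs if no imaging is done or the 6-month column is followed, and 1 if the 12-month column is followed.
- Through month 36: 4 + 3 × 0 = 4, up to 4 + 3 × 1 = 7.

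**Risk-specific participants (x and [x])**

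The table does not say whether the two body CTs are alternatives at a visit or are both done. I take a risk-specific participant to have at least one body CT at 6 months.

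- By month 12, if alternatives: 3 + 1 + 1 = 5. If both: 3 + 2 + 2 = 7.
- Through month 36, lowest (alternatives, no later imaging): 5 + 3 × 0 = 5.
- Through month 36, highest (both, imaging at all three later visits): 7 + 3 × 2 = 13.

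**Extremity X-rays** (x at baseline, [x] at 6 months, x at 12 months)

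- Non-risk: 2 sets by month 12; through month 36, 2 to 2 + 3 × 1 = 5.
- Risk-specific: up to 3 sets by month 12; through month 36, up to 3 + 3 × 1 = 6.

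**Set against section 4**

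| Item | Schedule or risk text | Carried into the risk assessment? |
|---|---|---|
| Radiation exposure from CT and X-ray | Disclosed in 4.1 | Yes, as an exposure only |
| Radiation risk to the participant | Not named | No |
| Number of CTs and X-rays | Only in the 3.3.2 table | No |
| Radiation risk to a fetus | Named in 4.1 | Yes, as the reason for the pregnancy rule |
| Life-threatening contrast reactions, rare | Named in 4.1 for CT and gadolinium | Named, then summed up in 4.3 as minimal or negligible |

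Section 4.3 therefore draws its conclusion from a list in which one recurring exposure has no stated consequence and no total, and in which another item is too serious for the word negligible.

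**A conflict within the count.** The paragraph that introduces the table also makes imaging depend on the history, physical examination and omics results. Section 3.1 describes follow-up imaging as modified and targeted by earlier findings. Both sit badly with x meaning all participants. The figure of 4 rests on the explicit rule for x. If that rule is not meant literally, the minimum is lower and the protocol does not say what it is.

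**The case against.** The strongest reply is that nothing is hidden. Section 4.1 discloses ionizing radiation under a heading on risks, describes CT contrast reactions including life-threatening ones, and the schedule is in the same document. The protocol is also under IRB review. This is right as far as it goes: the exposure and the contrast reactions are named, and it would be wrong to say the protocol conceals either. What it leaves unanswered is that no radiation risk to the participant is stated, no total is given, and 4.3 nevertheless relies on the description as complete.

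Some stronger readings are tempting, and the documents do not support them.

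- *The pregnancy rule proves that the radiation is hazardous to adults.* It does not. Concern for a fetus is compatible with a small risk to an adult. The rule shows only that the protocol names a radiation risk in one place and not in the other.
- *The cumulative dose shows that minimal is wrong.* The protocol gives no dose per scan and no threshold, so no dose figure can be tested.
- *Four CTs are certain for everyone.* This holds under the rule for x, subject to the conflict described above. The three baseline CTs may also share one session.
- *The consent form understates exposure, or the CRF omits dose.* Neither document is shown. Section 6.1 treats imaging reports as source documents that may be analysed.
- *The study cannot meet its objective without dose data.* Section 2.1 asks which modality contributes most to identifying deviations, not which has the best balance of yield against exposure.

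**Conclusion.** The point holds as a gap between the stated benefit/risk conclusion and the text and schedule it relies on. By the table's own rule, each participant has 4 CTs by month 12 and extremity X-rays at baseline and 12 months. Through month 36 the range is 4 to 7 CTs without risk-specific imaging and 5 to 13 with it. These figures rest on x meaning all participants. The width of the ranges comes from two things the protocol leaves open: whether the two body CTs are alternatives, and whether the optional later imaging is done.

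The word negligible also conflicts with the rare life-threatening reactions in section 4.1. It does not follow that the risk is high, that the minimal-risk label is necessarily wrong, or that the imaging should change. What follows is that section 4 does not yet support the conclusion drawn from it. This should be corrected because it is cheap and bears on what participants are told, although it alters no estimate or endpoint.

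**What to change.** - **Section 4.1:** state the number of CT and X-ray examinations scheduled by month 12 and by month 36, separately for non-risk and risk-specific participants, and name cumulative radiation as a risk to the participant.
- **Section 4.3:** drop the word negligible, so that the conclusion matches the risks listed.
- **Synopsis:** reconcile the minimal-risk wording with the imaging table and the risks in 4.1.
- **Section 3.3.2:** reconcile the rule that x means all participants with the statements there and in 3.1 that imaging depends on clinical and laboratory findings. State whether the two body CTs are alternatives at a visit.
- **Optional:** copy the scanner-reported dose of each CT to the CRF and report cumulative exposure descriptively.

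The cost is a wording amendment, a check that the consent text agrees with it, and, if the option is taken, one CRF field. The downside is that the stated benefit/risk becomes less favourable and the IRB may revisit the risk category. The imaging schedule itself is left as it is.

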## 5. Adverse Events

### 5.1. Definitions

An Adverse Event (AE) is a noxious and unintended event observed in, or reported by, a participant who is participating in (or has participated in) a clinical study, and/or received study medication, an experimental device, or study-related procedure. The event may be related temporally either to immediate or long-term use of a drug, device, or procedure. It may not necessarily be caused by a drug, device, or procedure. Any event meeting these criteria shall be considered an adverse event, regardless of whether or not it is considered study related. A pre-existing condition that worsens during the trial is considered an AE.

The following events will be considered as adverse events:

- Event directly related to study procedure
- Unintended event as a result of non-standard of care study tests, medications or procedures

A Serious Adverse Event (SAE) is defined as one that is fatal or immediately life-threatening, severely or permanently disabling, requires or prolongs in patient hospitalization, a congenital anomaly, cancer or overdose (intentional or accidental); or suggests a significant hazard, contraindication, side effect, or precaution. All SAEs will be followed by the investigator through trial end until resolution or until reaching a clinically stable status per the investigator's discretion.

The following adverse events will be handled as serious even if they do not meet the above criteria for designation as serious:

- Death
- Congenital abnormality
- Hospitalization
- Life threatening illness
- Intervention to prevent permanent damage

### 5.2. Pregnancy

WOCBP (see Protocol Synopsis for definition of WOCBP) must have a negative UPT prior to study enrollment and at each study visit. Prior to study enrollment, WOCBP must be advised of the importance of avoiding pregnancy at each visit. The subject must sign an informed consent form documenting this discussion.

WOCBP should be instructed that if they are pregnant, they will not be permitted to be enrolled and are subject to withdrawal from the study with a positive UPT at any visit, as per Section 3.2.3.

### 5.3. Reporting

The Puer study does not prescribe any pharmaceutical or medical device-based intervention. Any AEs are associated with blood draw/venipuncture and MRI examinations that may or may not include Gadolinium-based contrast agents will be reported.

Each patient will be observed and queried in a nonspecific fashion at each contact during the study for any new or continuing symptoms since the last contact. All adverse events will be reported on the appropriate CRF. Details will include the type of event, date of onset, duration, intensity, causality relationship to the study procedure (if applicable), and outcome. Wherever possible, a diagnosis rather than symptom(s) will be reported.

If an AE should occur, every attempt will be made to obtain as much information as possible about event evaluation and outcome. Documents of this follow-up will be maintained with the patient's study records.

If a SAE occurs, the participation in the study will be interrupted or discontinued at the investigator's discretion.

All protocol deviations will be reported to the WCG IRB.

All SAEs will be reported immediately to the WCG IRB and the FDA (if applicable).

Endpoints will be adjudicated by the Principal Investigator. A written report detailing the endpoint adjudication will be provided by the Principal Investigator.

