### 2.4. Exploratory Endpoints

[figure not shown]
- The number and change in the number of medications taken by an individual at 6 months, 12 months, 18 months, and 24 months after enrollment
- The number and change in the number of dietary supplements taken by an individual at 6 months, 12 months, 18 months, and 24 months after enrollment

- Number of unscheduled, urgent care/emergency department visits within 24 months and 36 months after enrollment
- Number of unscheduled hospital admissions within 24 months and 36 months after enrollment

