##### 3.2.3 Participant withdrawal criteria

A participant may be withdrawn from the study prior to completion for any of the following reasons:

- Adverse Event (AE)
- Death
- Physician decision
- Pregnancy at any visit
- Protocol deviation
- Other (e.g., any reason that may affect the outcome of the study or safety of participants)
- Participant no longer wants to participate (without penalty)

When a participant is withdrawn from the study for an AE (as defined in Section 5), when possible, the participant should be followed until resolution or stabilization of the AE.

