## 7. Statistical Considerations

By design, the study will not employ formal hypothesis testing. Study endpoints will be described using descriptive statistics, using means and standard deviations, medians with inter-quartile ranges, and other descriptive statistical methods, as appropriate.

Data from participants who discontinue the study prior to completion will only be considered through the date of withdrawal and will not be followed in the remaining longitudinal study endpoints.

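### Section 7 stops all endpoint follow-up at discontinuation, and Section 5.3 leaves unclear whether a participant may simply continue after an SAE, so a counted event can end its own later counting

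*Protocol*

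**What the plan says.** Four parts of the protocol bear on this.

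- **Action after an SAE (Section 5.3).** "If a SAE occurs, the participation in the study will be interrupted or discontinued at the investigator's discretion". Uninterrupted continuation is not named.
- **Withdrawal (Section 3.2.3).** "A participant may be withdrawn from the study prior to completion for any of the following reasons", and an adverse event heads the list. After withdrawal for an AE, where possible, "the participant should be followed until resolution or stabilization of the AE".
- **What is serious (Section 5.1).** The SAE definition covers an event that "requires or prolongs in patient hospitalization, a congenital anomaly, cancer or overdose (intentional or accidental"). Hospitalization appears again in a list introduced by "The following adverse events will be handled as serious even if they do not meet the above criteria for designation as serious". On relatedness the section says "Any event meeting these criteria shall be considered an adverse event, regardless of whether or not it is considered study related". The same section then gives a shorter list confined to events arising from study procedures or tests. The synopsis and the opening of Section 5.3 are also procedure-related.
- **Data after discontinuation (Section 7).** Data from participants who leave early "will only be considered through the date of withdrawal and will not be followed in the remaining longitudinal study endpoints". No reason for leaving is exempted.

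The endpoints affected are new deviations at 6, 12, 18 and 24 months (Section 2.2, main) and, in Section 2.4, exploratory counts that include "Number of unscheduled hospital admissions within 24 months and 36 months after enrollment".

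**The concern.** Section 7 makes leaving study procedures the same as leaving endpoint follow-up. That matters most when the reason for leaving is related to what is being counted. Hospitalization is both a seriousness criterion and an endpoint. Cancer is both a seriousness criterion and the kind of finding the study hopes to pick up early: Section 1.2 uses pancreatic cancer to justify six-monthly testing. A first admission, or a detected cancer, can therefore lead to a discontinuation after which that person's later admissions and deviations are no longer collected.

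Much of this loss is avoidable. Admissions, emergency visits, medications and supplements can all be obtained by history when imaging or blood draws are no longer safe. It is also not something an analysis plan can put right, because the protocol itself says the data will not be collected.

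**Working it through.** The protocol gives no admission, SAE or discontinuation rate and no figure to reproduce. The check is a reading of the text, one calculation that follows from the endpoint windows, and an illustration under assumed rates.

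**1. The chain of rules**

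1. On the broad wording of Section 5.1, an unrelated admission or cancer is an SAE.
2. Section 5.3 then has the investigator interrupt or discontinue participation. The verb is mandatory but the discretion clause follows it. The sentence can mean a forced choice between two actions, or a free choice whether to act at all. Only the first rules out simple continuation.
3. If the choice is discontinuation, Section 7 ends endpoint follow-up at that date.
4. The follow-up in Section 3.2.3, and the SAE follow-up in Section 5.1, track the event until it resolves or stabilizes. Neither restarts the counting of endpoints.

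**2. Window lost by one participant discontinued at month m**

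Unobserved share = (24 − m)/24 and (36 − m)/36. Deviation time points kept = those of 6, 12, 18 and 24 months reached, assuming the visit at month m is completed.

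| m | 24-month window unobserved | 36-month window unobserved | Deviation time points kept |
|---|---|---|---|
| 6 | 18/24 = 75% | 30/36 = 83% | 1 of 4 |
| 12 | 12/24 = 50% | 24/36 = 67% | 2 of 4 |
| 18 | 6/24 = 25% | 18/36 = 50% | 3 of 4 |

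These are per person. They say nothing about how many people are affected.

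**3. Illustration for the admission count (all rates assumed)**

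Assume the broad AE wording, a constant admission rate L per person-year that is equal across participants, and a probability d that an admission leads to discontinuation. Over T years the true mean count is L·T. The triggering admission is counted, so the recorded mean is (1 − exp(−d·L·T))/d, and the shortfall is 1 − recorded/true.

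| L | T = 2, d = 0.5 | T = 2, d = 1 | T = 3, d = 0.5 | T = 3, d = 1 |
|---|---|---|---|---|
| 0.05 | 2.5% | 4.8% | 3.7% | 7.1% |
| 0.10 | 4.8% | 9.4% | 7.1% | 13.6% |
| 0.20 | 9.4% | 17.6% | 13.6% | 24.8% |

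At d = 0 nothing is lost. Worked example, L = 0.10 and d = 0.5: (1 − exp(−0.10))/0.5 = 0.1903 against 0.20 at 24 months, and (1 − exp(−0.15))/0.5 = 0.2786 against 0.30 at 36 months. With 10,000 participants, the most the protocol allows, that is 1,903 of 2,000 and 2,786 of 3,000 admissions.

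**4. Would a person-time rate repair it?**

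Under a constant, equal rate, yes: the rate per person-year observed recovers L. If admissions cluster in the same people, no. Assume gamma-distributed individual rates with mean 0.10 and relative variance 1, and d = 0.5.

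- T = 2: recorded = (1 − 1/1.10)/0.5 = 0.1818; person-years = ln(1.10)/0.05 = 1.9062; rate = 0.0954, which is 4.6% low.
- T = 3: recorded = (1 − 1/1.15)/0.5 = 0.2609; person-years = ln(1.15)/0.05 = 2.7952; rate = 0.0933, which is 6.7% low.

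**The case against.** A reader might infer that Section 5.3 contradicts Section 3.2.3 by making removal compulsory where 3.2.3 only permits it. The documents do not support that. Interruption is not withdrawal, and discontinuation under 5.3 is left to the investigator, so withdrawal after an SAE is optional under both sections and both can be obeyed together. What remains is an ambiguity about continuing without a pause.

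It can also be said that 5.3 is not the operative rule. Section 3.2.3 already allows withdrawal for any AE or by physician decision, and Section 7 stops follow-up whatever the reason. Deleting the sentence in 5.3 would leave the same exposure. This is right, and it is why the main change belongs in Section 7.

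Further, the loss needs several things together: the broad AE wording must govern, the investigator must choose discontinuation over interruption, and later events must have been there to miss. The procedure-related wording in the synopsis, the short list in 5.1 and the opening of 5.3 would largely avoid the problem. Nothing suggests investigators would routinely discontinue someone for an unrelated admission in a study with no intervention that accepts any medical history. Interruption alone does not trigger Section 7, and a participant who resumes can report events from the pause, since history is taken at every visit. All of this stands and keeps the point small.

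It does not remove the point. The broad wording is explicit. Section 5.3 also asks about any new or continuing symptoms and records causality to the study procedure only where applicable. How truncated follow-up is analysed may be left to an analysis plan, but whether the data exist is settled in Section 7.

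**Conclusion.** The concern holds as a modest improvement to a stated rule. Section 7 ends endpoint follow-up for everyone who discontinues, and Section 5.3 does not make clear that a participant may continue after an SAE. On the broad AE wording, and if the investigator discontinues, an admission or cancer stops the collection of that person's later admissions and later deviations.

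The percentages for admissions should not be read as an estimate of bias in this study. They run from zero to 24.8% depending on assumed rates and on an assumed chance of discontinuation, and the protocol supports none of these values. Neither the size nor the direction of any effect on the reported summaries can be derived from it. The triggering event is kept, the admission endpoint is exploratory, the study is descriptive so no test is affected, and nothing is lost if nobody is discontinued.

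**What to change.** Amend Section 7, with matching words in Section 3.2.3, so that participants whose study procedures are stopped by the investigator remain in follow-up, unless they withdraw consent. Follow-up would cover endpoints obtainable by history (admissions, emergency visits, medications, supplements) and any modality that is still safe. Reword the sentence in Section 5.3 to say that after an SAE participation may continue, be interrupted or have procedures stopped, at the investigator's discretion.

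This costs a sentence in 5.3 and short edits in the other two sections. Safety discretion is unchanged. The downside is that some later visits will be incomplete, with slight extra effort to keep in contact.
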